5.0 HEALTH RESEARCH ETHICS

5.1 General considerations

This study only involves questionnaire and medical records and is hence exempt from approval from The Health Research Ethics Committee and can be implemented without permission from the Ethics Committee according to Danish legislation (Health Research Ethics Committee Act § 1, paragraph 1).

Nevertheless, we will conduct this study obeying high health research ethical standards. Prior to screening, all potential trial participants are informed, both orally and in writing, about the purpose of this study, its process, and costs and benefits of participation. All participants are informed of their rights to withdraw from the study at any time without this impacting on any

future investigations and/or treatments at any site or by any of the members of the study group. After the information is delivered, read and understood, voluntary informed consent is given by the participant by signing a consent form before trial participation can take place.

5.2 Written information and informed consent

A written consent to participation in the study is given after verbal explanation and consent.

A written information material and informed consent form (ICF) have been prepared (both attached as appendices, files in Danish). By signing the ICF the participant accepts to be contacted by an investigator (or his/her delegate) and authorise him/her to collect relevant information from the participant's hospital record according to Danish legislation (Act on Processing of Personal Data).

The ICF must be signed and dated by the participants prior to participation in the study. A copy of the form is provided to the participants. A note will be made in the patients' hospital records about participation in the study and signed authorisation to collect relevant data from the records.

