Conflict of interest declaration

None declared.

SUMMARY

Background: Overweight is a main and modifiable risk factor for developing knee osteoarthritis (OA). Studies indicate a beneficial effect of weight loss on the symptoms of knee OA. The Intensive diet vs Knee Arthroplasty (INKA) trial is a RCT, which aims to assess weight loss as a non-inferior intervention and/or an alternative to surgical knee arthroplasty in overweight and obese patients suffering from knee OA. As RCTs carry a risk for selection bias and thereby risk for low external validity, comparison of the recruited trial participants and the invited participants, who decline trial participation will enable assessment of the external clinical validity and generalizability of the INKA trial

Objective: The objective of this study is to compare baseline characteristics of overweight knee OA patients accepting vs. declining enrolment in the INKA trial to explore if enrolled patients differ systematically from the declining participants with respect to both measured as well as unmeasured baseline characteristics.

Design: Cross-sectional study collecting baseline characteristics of patients with Knee OA eligible for enrolment in the INKA trial, whether accepting or declining enrolment.

Setting: Potential trial participants will be identified during their routine visits in the orthopaedic outpatient clinics at Copenhagen University Hospital Bispebjerg-Frederiksberg and Copenhagen University Hospital Amager-Hvidovre.

Participants: Adults ≥ 18 years old, obese ($BMI \geq 30 \text{ kg/m}^2$), with an indication for primary knee arthroplasty (unicondylar or total arthroplasty) due to knee OA are included either with consent or refusal to participation in the INKA trial. We will recruit 400 patients in total, 200 in each group.

Measurements: Baseline characteristics for the 2 groups are obtained extracting data from the participants' medical records including questionnaires answered by all patients, of which the main is The Oxford Knee Score (the primary outcome for INKA participants).

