4.3 Participants

All patients found eligible in INKA study (inclusion criteria for INKA) and accepting and declining enrolment in the INKA study are invited to participate in our study. We report the number of patients assessed for eligibility and reasons of exclusion. Study participants will be adults (i.e. at

least 18 years old), have a diagnosis of knee osteoarthritis with an indication for primary knee arthroplasty (unicondylar or total arthroplasty), and be obese ($BMI \geq 30 \text{ kg/m}^2$). An individual will be eligible for study participation if he/she meets the following criteria:

1. Age 18 or more
2. A clinical and radiological diagnosis of knee OA
3. $BMI \geq 30 \text{ kg/m}^2$
4. Motivated for weight loss as by the provided program
5. Signed informed consent.

A possible participant will, however, be excluded from the study if he/she meets any of the following criteria:

1. The scheduled surgery is for revision of an existing prosthesis
2. Planned surgery for more than one knee within the observation period
3. KA indication due to sequelae of fracture(s)
4. Injection of medication or substances in the target knee within 3 months prior to participation
5. Immuno-inflammatory arthritis as cause of the knee OA
6. Current systemic treatment with glucocorticoids equivalent to $> 7.5 \text{ mg}$ of prednisolone/day
7. Previous or planned obesity surgery
8. Inability to understand or read Danish incl. instructions and questionnaires
9. Any other condition or impairment that, in the opinion of the investigator (or his/her delegate), makes a potential participant unsuitable for participation or which obstruct participation.

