4.8 Bias and confounding variables

Confounding is an important concept in epidemiology, because, if presents, it can cause an over- or underestimate of the observed association between exposure and health outcome. The distortion introduced by a confounding factor can be large, and it can even change the apparent direction of an effect. However, unlike selection and information bias, it can be adjusted for in the analysis.

The challenge with observational data (like the proposed comparison) is that the groups (INKA vs nINKA) are not applied randomly, leading to selection bias and thus potentially confounding variables. For example, when we study the impact entering a “promising weight loss trial” before having direct access to a KA, and we compare the outcome among those (who accept the invitation to join the INKA trial) versus all of those who declined, we would potentially have some selection bias, as those who decline are different per definition. The difference can range from baseline characteristics that would influence the outcome; i.e., an advanced disease stage that make any potential delay of the surgery intolerable, or failure/ineffectiveness of previous weight loss trials. Or it can be a characteristic with neglectable effect on the outcome, ie., not having the time or the desire to be included in a clinical trial. Improved confounding variable balance (i.e. de-confounding) between INKA and nINKA groups can be achieved by matching observations from each group based on the propensity score, which in this case would be the probability that a patient accept participation in INKA given the observed covariates.

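### nINKA contains only decliners who also sign this study's consent form, so its comparisons describe consenting decliners, with bias of unknown size and direction

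*Combined protocol and SAP*

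**What the plan says.** The objective (section 3.0) is to compare patients who accept INKA with patients who decline it. Section 4.9 treats the crude comparisons as evidence on INKA's generalisability, with standardised differences read against 0.2 (possible imbalance) and 0.8 (incomparable).

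Entry to this study runs through its own consent:

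- Section 4.3: eligible patients "accepting and declining enrolment in the INKA study are invited to participate in our study", so decliners are invited, not included automatically. Entry criterion 5 is "Signed informed consent", with no exception for decliners.
- Section 5.2: "The ICF must be signed and dated by the participants prior to participation in the study". By signing, patients agree to be contacted by the investigator and "authorise him/her to collect relevant information from the participant's hospital record according to Danish legislation".
- Summary, Participants: patients "are included either with consent or refusal to participation in the INKA trial". The refusal meant here is refusal of INKA; the sentence does not waive consent to this study.

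On people who do not enter, section 4.3 promises a count of those screened and the grounds for leaving patients out, and section 7.0 lists a screening log. Section 4.8 discusses how acceptors and decliners may differ. It does not discuss which decliners reach the nINKA group.

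**The concern.** The study exists to detect selection into INKA, yet its comparison group passes through a second selection step: consent to research. Section 4.8 itself gives as one reason for declining "not having the time or the desire to be included in a clinical trial". A patient who declines INKA for that reason may well decline this study too, and then no covariate can be extracted.

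The nINKA column of Table 1 would thus describe decliners willing to have their data used. If they differ from the other decliners, a variable could stay below 0.2 and be read as reassuring when the full decliner group would have been flagged, or be flagged when the full group would not. Either error bears on what the study may say about INKA's generalisability.

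**Working it through.** **Plan figures.** The documents give no consent share and no figure for patients who refuse both studies, so there is no plan figure on this point to reproduce. The only power figures in the readable text concern INKA itself. They reproduce (one-sided 0.025, margin 4, SD 8, t-based: 90.3% with 86 per group, 94.0% with 100 per group) and are not affected.

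**Step 1: who supplies data.** Section 4.3 (invitation, criterion 5) and section 5.2 (form signed first; form authorises record extraction) together leave three groups of eligible patients: acceptors, consenting decliners, and decliners who refuse this study as well. The third group has no covariate data.

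**Step 2: tipping value.** Let c be the share of decliners who consent, d_obs the standardised difference between acceptors and consenting decliners, and d_ref that between acceptors and double refusers. Signs are set so that d_obs is positive. Assume similar variances and that almost all acceptors consent. Then

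d_all ≈ c·d_obs + (1 − c)·d_ref,

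and d_all reaches 0.2 when

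d_ref = (0.2 − c·d_obs)/(1 − c).

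| assumed c | d_obs = 0.15 | d_obs = 0.05 |
|---|---|---|
| 0.5 | (0.2 − 0.075)/0.5 = 0.25 | (0.2 − 0.025)/0.5 = 0.35 |
| 0.7 | (0.2 − 0.105)/0.3 = 0.32 | (0.2 − 0.035)/0.3 = 0.55 |
| 0.9 | (0.2 − 0.135)/0.1 = 0.65 | (0.2 − 0.045)/0.1 = 1.55 |

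Mixing two subgroups widens the decliner variance slightly. With unit within-group SD, v = 1 + c(1 − c)(d_obs − d_ref)² and d_all = [c·d_obs + (1 − c)·d_ref]/√((1 + v)/2). For c = 0.9, d_obs = 0.15 and d_ref = 0.65, v = 1.0225 and d_all = 0.2/√1.01125 = 0.199. The simple formula is adequate here.

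**Step 3: range for all decliners.** Using the variance-adjusted formula, with d_ref assumed to lie between 0 and 0.8:

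- d_obs = 0.15, 20% refuse both: d_all runs from 0.12 to 0.28.
- d_obs = 0.15, 50% refuse both: 0.075 to 0.46.
- d_obs = 0.20 (flagged), double refusers like acceptors (d_ref = 0): 0.16 if 20% refuse both, 0.10 if 50% do.

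The first two ranges span 0.2. The third case shows a flag that the full decliner group would not have produced.

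**Step 4: direction.** A simulation of 2 million patients used two standard-normal traits, knee severity S and research willingness W. Half decline INKA, those with the higher values of 0.3·S − 0.6·W + standard-normal noise. The 10% or 25% least willing refuse this study, so 17% to 41% of decliners refuse both. All of these settings are assumptions.

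| trait compared | correlation of S and W | all patients | consenting only (10% / 25% refuse) |
|---|---|---|---|
| willingness | 0 | 0.866 | 0.745 / 0.643 |
| severity | 0 | 0.405 | 0.422 / 0.437 |
| severity | −0.3 | 0.645 | 0.596 / 0.563 |
| severity | −0.6 | 0.894 | 0.779 / 0.690 |

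Willingness-type traits are understated. Severity is slightly overstated if unrelated to willingness, and understated if sicker patients are less willing. The documents do not say which holds.

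**The case against.** **Direction.** A reader might infer that the second consent pulls all differences toward zero. The documents do not support that. Most clinical variables in section 4.4 (OKS, KOOS-12, PGA, EuroQoL, analgesics) concern severity or health status, and none measures research willingness directly. Section 4.8 places lack of time or interest among traits it regards as having next to no bearing on outcome. If double refusers are mainly such patients, losing them could leave the more severe decliners in nINKA and enlarge the severity differences. This objection stands.

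**Traceability.** A reader might infer that double refusers vanish from the record. That is too strong. A patient who does not sign fails criterion 5 and may appear among the exclusion reasons, in the screening log, or in Figure 1, which was not available for review. What remains is that the readable text promises no separate count. A count alone would also supply neither a comparison nor a limit on the conclusion.

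**Contradiction.** Section 4.8 speaks of those "who accept the invitation to join the INKA trial) versus all of those who declined", which could be read as defining the population and clashing with section 4.3. It stands in an illustration of confounding; section 4.3 sets the population. The wording is loose, not a contradiction of the design.

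**Sequence.** The documents do not state the order or number of forms, and section 5.1 places the information about this study before screening. That the consent step filters almost only decliners is therefore plausible but not documented.

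**Size.** An assumed d_obs of 0.15 is already close to the threshold; at 0.05 the tipping values are much larger. With 200 per group the standard error of d is about √(2/200) = 0.10, so a shift of 0.05 is half a standard error. The burden is only questionnaires and record data, so a high c is possible. All of this is fair, and it is a reason to report c, not to leave it out.

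**Conclusion.** The concern holds in limited form. As written, nINKA consists of INKA decliners who also consent to this study, and no readable section handles that second selection. Comparisons at 0.2 apply to consenting decliners. The bias has unknown size and direction: understatement is plausible for motivation and illness-perception variables, and knee-severity differences could be understated or overstated.

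The size rests on assumed values of c and d_obs. With d_obs = 0.15, double refusers would need to differ from acceptors by 0.25, 0.32 or 0.65 (c = 0.5, 0.7 or 0.9) to bring the full decliner group to 0.2. If c is high and d_obs small, the problem is minor; if c is near one half, a reading at 0.2 is fragile. The study remains useful, and INKA's own design is not affected.

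**What to change.** 1. In the existing screening log, count separately the acceptors, the consenting decliners and the eligible patients who refuse both. Report the consent share in each arm, acceptors included. Set this up during recruitment, since uncounted refusers may not be recoverable later.
2. For each baseline variable, report the tipping value (0.2 − c·d_obs)/(1 − c) beside the standardised difference. For a variable already at or above 0.2, the same formula gives the value below which the flag would disappear.
3. Describe the comparison group throughout as decliners who consented to data collection, including in section 4.8. Do not conclude generalisability for a variable whose tipping value is small, and state before analysis what will count as small.
4. Compare age band, sex and hospital for double refusers only if such anonymous data may lawfully be kept. Sections 5.2 and 6.2 tie data collection to the patient's authorisation or permission, so this needs a legal check. If the answer is no, items 1 to 3 still work.

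The cost is a change of wording, a little more logging and one extra table column, at the price of a slightly weaker generalisability claim.

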6.0 REGULATORY STANDARDS

6.1 Notification to the Danish Data Protection Agency

Because the study is carried out at hospital departments, it is regarded as "public" in accordance with the Data Protection Agency guidance. The study will be notified to the Data Protection Agency.

6.2 Participant confidentiality

Participant medical information obtained by this study is confidential, and disclosure to third parties other than those noted below is prohibited.

With the participant's permission, medical information may be collected for scientific use and shared with his or her personal physician or with other medical personnel responsible for the participant's welfare.

When the data from this study are published, the presentation format will not include names, recognizable photos, personal information or other data which compromises the anonymity of participating participants.

6.3 Quality assurance

All data will be entered into a study database for analysis and reporting. Any data captured electronically will be stored electronically in a separate database according to standard procedures of Region Hovedstaden. Upon completion of data entry, the databases will be checked to ensure acceptable accuracy and completeness. System backups and record retention for the study data will be consistent with Region Hovedstadens standard procedures.

Individuals involved in study evaluations will be trained to perform the efficacy evaluations and activity measurements described in the protocol.

6.4 Financing and insurance information

The study has not received any specific funding. If funding is obtained, the amount and donor will be disclosed on the written information material.

The participants are insured by the Danish Patient Insurance Association. Financing and insurance issues are addressed in the written information material.

7.0 LIST OF APPENDICES

- Questionnaires
- Written information material (In Danish)
- Informed consent form (In Danish)
- Screening log (In Danish)

